5.3 Discontinued Subjects

Discontinued subjects are those who withdraw or are withdrawn from the study after signing the informed consent, including screen failures. Subjects may discontinue from the study at any time for any reason. Subjects may also be discontinued from the study at any time if, in the opinion of the Investigator, their continued participation poses a risk to their health. Discontinued subjects will not be replaced (ie, their subject numbers will not be re-assigned/re-used).

Should a subject exhibit any clinically relevant signs, symptoms, or other clinical observations that possibly could be associated with suspected sensitivity or intolerance to one of the study treatments, the Investigator must document those observations on an AE Form.

Any subject who exits early from the study (excluding screen failures) must undergo all procedures outlined at Visit 3, as applicable.

Document: TDOC-0054506 Version: 1.0; CURRENT; Most-Recent; Effective

Status: Effective Page 22 of 38

The Investigator must document the reason for study or treatment discontinuation in the subject's case history source documents.

To ensure the safety of all subjects who discontinue early, Investigators must assess each subject and, if necessary, advise them of any therapies and/or medical procedures that may be needed to maintain their health.

5.4 Clinical Study Termination

The Study Sponsor reserves the right to close the investigational site or terminate the study in its entirety at any time, for reasonable cause.

If the clinical study is prematurely terminated or suspended by the Study Sponsor:

- The Study Sponsor must:
 - Immediately notify the Investigator(s) and subsequently provide instructions for study termination.
 - Inform the Investigator and the regulatory authorities of the termination/suspension and the reason(s) for the termination/suspension, as applicable.
- The Investigator must:
 - Promptly notify the IRB of the termination or suspension and of the reasons.
 - Provide subjects with recommendations for post-study treatment options as needed.

The Investigator may terminate a site's participation in the study for reasonable cause.

6 ANALYSIS PLAN

Continuous variables will be summarized using the number of observations, mean, standard deviation, median, minimum, and maximum. Categorical variables will be summarized with counts and percentages from each category. Any deviations to this analysis plan will be updated during the course of the study as part of a protocol amendment or will be detailed in the clinical study report.

Document: TDOC-0054506 Version: 1.0; CURRENT; Most-Recent; Effective

Status: Effective Page 23 of 38

6.1 Subject Evaluability

The final subject evaluability will be determined prior to breaking the code for masked treatment sequence assignment and locking the database, based on the Deviations and Evaluability Plan.

6.2 Analysis Data Sets

6.2.1 Safety Analysis Set

Safety analyses will be conducted using the safety analysis set on a treatment-emergent basis. As such, the safety analysis set will include all subjects/eyes exposed to any study lenses evaluated in this study. For treatment-emergent safety analyses, subjects/eyes will be categorized under the actual study lenses exposed.

6.3 Demographic and Baseline Characteristics

Demographic information (age, sex, ethnicity, race) will be summarized on the Safety
Analysis Set Baseline data pertaining to habitual lens
will be summarized on the Safety Analysis Set as well.

6.4 Effectiveness Analyses

This study defines one primary endpoint Data for DD T2 will be summarized according to the crossover control worn per each parallel group. The Safety Analysis Set will serve as the primary set for all effectiveness analyses.

6.4.1 Primary Effectiveness

The primary objective of this study is to evaluate the overall performance of DD T2 lenses when compared to Oasys 1-Day, MyDay and 1-Day Acuvue Moist. The primary endpoint is the subjective rating on overall quality of vision, collected binocularly on a scale of 1 (Poor) to 10 (Excellent).

6.4.1.1 Statistical Hypotheses

No inferences are to be made on the primary effectiveness endpoint/s, therefore no hypotheses are formulated.

6.4.1.2 Analysis Methods

[figure not shown]
Descriptive statistics will be provided.

Document: TDOC-0054506 Version: 1.0; CURRENT; Most-Recent; Effective

Status: Effective Page 24 of 38

6.4.2 Secondary Effectiveness

No secondary objective or endpoint is defined for this study.

Document: TDOC-0054506 Version: 1.0; CURRENT; Most-Recent; Effective

Status: Effective Page 25 of 38

6.5 Subgroup Analyses

It is not expected that demographic or baseline characteristics will have an impact on the study results in this study. No subgroup analyses are planned.

6.6 Handling of Missing Data

All data obtained in evaluable subjects/eyes will be included in the analysis. No imputation for missing values will be carried out for the primary analysis.

6.7 Multiplicity

No multiplicity adjustment needs to be considered for the effectiveness endpoints since no formal hypothesis testing will be conducted.

6.8 Safety Analysis

The safety endpoints for this study are AEs, biomicroscopy findings, and device deficiencies. Data for DD T2 will be summarized according to the crossover control worn per each parallel group.

Descriptive summaries (counts and percentages) for ocular and nonocular AEs will be presented by Medical Dictionary for Regulatory Activities Preferred Terms. AEs leading to study discontinuation, significant non-serious AEs, and SAEs will be identified. Individual subject listings will be provided, as necessary.

Individual subject listings will be provided for AEs that occur after signing informed consent but prior to exposure to study lenses.

Each biomicroscopy parameter will be tabulated by its grade. For each biomicroscopy parameter, counts and percentages of eyes that experience an increase of ≥ 2 grades from Baseline (Visit 1) to any subsequent visit will be presented. A supportive listing will be generated which will include all biomicroscopy data from all visits for these eyes experiencing the increase.

Two listings (prior to exposure of study lenses and treatment-emergent) of device deficiencies, as recorded on the Device Deficiency Form, will be provided. Additionally, each device deficiency category will be tabulated.

No inferential testing will be done for safety analysis.

Document: TDOC-0054506 Version: 1.0; CURRENT; Most-Recent; Effective

Status: Effective Page 26 of 38

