1 PROTOCOL SYNOPSIS

Trial Sponsor	Alcon Research, Ltd.
	[name]
Name of Test Product	DD T2
Name of Control	ACUVUE OASYS® Brand Contact Lenses 1-Day with
Products	HydraLuxe™ Technology (Oasys 1-Day)
	CooperVision® MyDay® (MyDay)
	• 1-Day ACUVUE® MOIST (Moist)
Title of Trial	Clinical Comparison of 4 Daily Disposable Soft Contact Lenses
Protocol Number	CLE383-C004
Number of Sites	~3
Country	US
Planned Duration of	~20 days total duration
Exposure	• Test Product: 8 days (-1/+2 days)
1 -	 Control Products: 8 days (-1/+2 days)
Number of Subjects	Target to complete: 60 (20 per each parallel group)
	Planned to enroll: ~66 (~22 per each parallel group)
Study Population	Volunteer subjects aged 18 or over who are soft daily disposable
	contact lens wearers (excluding current Oasys 1-Day, MyDay, and
	Moist wearers), have at least 3 months of contact lens wearing
	experience, and who wear their habitual lenses at least 5 days per week
	and at least 8 hours per day.
Objectives	The primary objective of this study is to evaluate the overall
-	performance of DD T2 lenses when compared to Oasys 1-Day, MyDay,
	and Moist lenses.
Endpoints	Primary Effectiveness
_	Overall quality of vision

Document: TDOC-0054506 Version: 1.0; CURRENT; Most-Recent; Effective

Status: Effective Page 3 of 38

	Safety		
	• AEs		
	Biomicroscopy findings		
	Device deficient		
Assessments	Effectiveness		
Assessments	- VA (Snellen distance)		
	- VA (Shehen distance)		
	Occupation of civic		
	- Overall quality of vision	n	
	Safety		
	- AEs		
	- Biomicroscopy		
	- Device deficiencies		
Study Design	□ Prospective	Single-masked	
study Design	Single group	(trial subject)	
	Parallel group	Single-masked (Investigator)	
	Crossover	Double-masked	
	Other	Open-label	
		Other	
	Contralateral	Randomized	
	Bilateral	Kandonnized	
	Monocular lens wear		
		over group study design. In each arm, the	
		pared to one of 3 chosen control lenses.	
		l be randomized to 1 of the 6 lens	
		sover sequences of test vs. control within	
		Subjects will wear the assigned study	
		nately 1 week before crossing over into	
	the assigned study Lens 2 bilat same design will be scheduled	erally for approximately 1 week. This for each of the 3 arms.	

Document: TDOC-0054506 Version: 1.0; CURRENT; Most-Recent; Effective

Status: Effective Page 4 of 38

	Study Visits:			
	1. Baseline/Dispense Lens 1			
	2. Day 8 (-1/+2 days) follow-up Lens 1/Dispense Lens 2			

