4 TREATMENTS ADMINISTERED

This is a 3-arm, parallel, crossover group study design. In each arm, the test lens will be evaluated compared to 1 of 3 chosen control lenses. Subjects will be randomized to 1 of the 6 lens sequences, as described below:

Sequence 1: DD T2 \rightarrow Oasys 1-Day

Sequence 2: Oasys 1-Day \rightarrow DD T2

Sequence 3: DD T2 \rightarrow MyDay

Sequence 4: MyDay \rightarrow DD T2

Sequence 5: DD T2 \rightarrow Moist

Sequence 6: Moist \rightarrow DD T2

Document: TDOC-0054506 Version: 1.0; CURRENT; Most-Recent; Effective

Status: Effective Page 13 of 38

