1.3 Randomization

A member of the Randomization Programming group at Alcon who is not part of the study team will generate the randomized allocation schedule(s) for study lens sequence assignment. Randomization will be implemented in iMedidata Balance.

Qualifying subjects will be randomized in a 1:1:1:1:1 manner to one of 6 lens sequences consisting of the test lens and a control lens as described below. For each sequence, subjects wear 1st lens then crossover to 2nd lens.

Sequence 1: DD T2/Oasys 1-Day

Sequence 2: Oasys 1-Day/DD T2

Sequence 3: DD T2/MyDay

Sequence 4: MyDay/DD T2

Sequence 5: DD T2/Moist Sequence 6: Moist/DD T2

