2.1 Safety Analysis Set

[figure not shown]
Safety analyses will be conducted using the safety analysis set on a treatment-emergent basis. As such, the safety analysis set will include all subjects/eyes exposed to any study lenses evaluated in this study. For treatment-emergent safety analyses, subjects/eyes will be categorized under the actual study lens exposed in the corresponding lens sequence.

Adverse events occurring from the time of informed consent but prior to first exposure to study lenses will be summarized in subject listings.

Document: TDOC-0054657 Version: 1.0; CURRENT; Most-Recent; Effective

Status: Effective

4 Effectiveness Analysis Strategy

This study defines one primary endpoint Data for DD T2 will be summarized according to the crossover control worn per each parallel group. The Safety Analysis Set will serve as the primary set for all effectiveness analyses.

Continuous variables will be summarized using the number of observations, mean, standard deviation, median, minimum, and maximum. Categorical variables will be summarized with counts and percentages from each category.

All data obtained in evaluable subjects/eyes will be included in the analysis. No imputation for missing values will be carried out for the primary analysis.

A listing of selected effectiveness data will also be provided.

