5.2 Safety Hypotheses

There are no formal safety hypotheses in this study. The focus of the safety analysis will be a comprehensive descriptive assessment of safety endpoints listed in Section 5.1.

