5.3.1 Adverse Events

The applicable definition of an AE is in the study protocol. All AEs occurring from when a subject signs informed consent to when a subject exits the study will be accounted for in the reporting.

Analysis and presentation of pre-treatment AEs will be separated from treatment-emergent AEs occurring during the study period. A pre-treatment AE is an event that occurs after signing informed consent but prior to exposure to study lenses. The period for treatment-emergent AE analysis starts from exposure to study lenses until the subject completes or is discontinued from the study. Each AE will be summarized under the exposed lens based upon the event onset date/time, up until the start of the next lens in the crossover sequence.

The following tables and supportive listings will be provided:

- Incidence of All Ocular Treatment-Emergent Adverse Device Effects
- Incidence of All Ocular Treatment-Emergent Adverse Events, Not Related
- Incidence of All Ocular Treatment-Emergent Adverse Events, Overall
- Incidence of All Nonocular Treatment-Emergent Adverse Device Effects
- Incidence of All Nonocular Treatment-Emergent Adverse Events, Not Related
- Incidence of All Nonocular Treatment-Emergent Adverse Events, Overall
- Listing of All Ocular Treatment-Emergent Adverse Events
- Listing of All Nonocular Treatment-Emergent Adverse Events
- Listing of All Ocular Pre-Treatment Adverse Events
- Listing of All Nonocular Pre-Treatment Adverse Events

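### Does splitting DD T2 safety data by control lens leave the new lens without a result for everyone who wore it?

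*Protocol*

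**What the plan says.** Protocol 4 sets up three parallel arms, each a two-period crossover: "In each arm, the test lens will be evaluated compared to 1 of 3 chosen control lenses". SAP 1.3 assigns subjects to "one of 6 lens sequences consisting of the test lens and a control lens as described below". DD T2 therefore appears in every sequence, first in three and second in the other three. The Protocol synopsis plans 20 completers and about 22 enrolled per parallel group, 60 and about 66 in all.

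For safety, Protocol 6.8 gives the column rule: "Data for DD T2 will be summarized according to the crossover control worn per each parallel group". It asks for counts and percentages of AEs, counts and percentages of eyes with a biomicroscopy increase of two or more grades, and a tabulation of device deficiencies by category. It rules out inferential testing.

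The SAP carries the same column sentence in section 4, on effectiveness, but does not repeat it in section 5, on safety. Two other SAP sentences bear on the layout:

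- SAP 2.1, the analysis set to which SAP 5.3 refers, has subjects and eyes "categorized under the actual study lens exposed in the corresponding lens sequence".
- SAP 5.3.1 states: "Each AE will be summarized under the exposed lens based upon the event onset date/time", with attribution ending when the next lens starts.

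SAP 5.2 describes the aim: "The focus of the safety analysis will be a comprehensive descriptive assessment of safety endpoints".

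**The concern.** DD T2 is the lens in development, and Protocol 3.3 allows that it may carry unknown risks. The most basic safety figure for such a product is the incidence of each event among everyone exposed to it, and no visible text names that figure as a planned result. The word 'Overall' in the SAP 5.3.1 table titles does not supply it: it stands beside device effects and unrelated events, so it means all causalities.

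The SAP wording also seems to leave the layout open. Attribution to the exposed lens (SAP 5.3.1) could be read as one DD T2 column. Attribution within the lens sequence (SAP 2.1) could be read as three. Two programmers might then build different tables. At stake would be percentages for the new lens that rest on about a third of the available subjects, and doubt about which table was intended.

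**Working it through.** **Column sizes.** From the synopsis, 3 × 20 = 60 to complete and 3 × 22 = 66 to enroll. Both agree with the stated totals, and the implied allowance is 6/66 = 9.1%. A split DD T2 column holds about 20 to 22 subjects and a pooled one about 60 to 66. These are planning figures. Enrollment is counted from consent (Protocol 5.1.1), and a subject in sequence 2, 4 or 6 who leaves in the first period never wears DD T2, so the number exposed may be lower.

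**Apparent cost of the split.** With zero events in n subjects, the one-sided 95% upper limit is 1 − 0.05^(1/n).

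| | Per column | Pooled |
|---|---|---|
| Enrolled | n = 22: 12.7% | n = 66: 4.4% |
| Completed | n = 20: 13.9% | n = 60: 4.9% |

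These limits are correct as arithmetic, but neither document visibly plans a confidence limit for safety. They compare two versions of an output that is not in the plan.

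**Whether anything is lost.** Each subject is in one parallel group, so the three DD T2 groups share no subjects or eyes. If x₁, x₂, x₃ subjects out of n₁, n₂, n₃ have an event, the pooled incidence is exactly (x₁ + x₂ + x₃)/(n₁ + n₂ + n₃), with no double counting. For example, 1/22 in each column gives 3/66 = 4.5%. Protocol 6.8 asks for counts as well as percentages for AEs and biomicroscopy, so the numerators are on the page. Counts of eyes and of device deficiencies add in the same way.

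**Whether an event is harder to see.** For a true rate p, the chance of at least one event in some column is 1 − ((1 − p)^22)³ = 1 − (1 − p)^66, which is the pooled chance. The documents give no event rates, so these are assumed:

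| Assumed rate | One column, n = 22 | Three columns together | Pooled, n = 66 |
|---|---|---|---|
| 2% | 35.9% | 73.6% | 73.6% |
| 5% | 67.7% | 96.6% | 96.6% |

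Comparing the first column of figures with the last would suggest a large loss, but a reader of the report sees all three columns and the listings.

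**Whether the layout is really open.** Set side by side:

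- Protocol 6.8 states the column rule for safety outright.
- The SAP says on its cover and in section 9 that it is based on Protocol Version 1.0.
- SAP 2.1 adds the reference to the lens sequence, which Protocol 6.2.1 lacks and which leans toward the split.
- SAP 5.3.1 assigns an event to a period by its onset. It concerns which lens is charged with the event, not how many columns a table has.

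No SAP sentence contradicts Protocol 6.8.

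**The case for a change.** The best case for a change is that it would cost little and that DD T2 is the lens of interest. A printed total over all exposed subjects is more convenient than adding three integers per row across nine tables (six for AEs, two for biomicroscopy, one for device deficiencies). It would also show the number actually exposed to DD T2. A comprehensive descriptive assessment might be expected to include it, and SAP section 5 could have repeated the column rule as section 4 does.

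Part of this stands. The visible text does not state an all-exposed DD T2 incidence, and SAP section 5 lacks a cross-reference. A programmer can supply both from Protocol 6.8 when the table shells are drawn.

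The rest does not amount to a defect. The split follows the design and the objective: it sets DD T2 beside the control worn by the same subjects, which is the comparison that each arm was built to make. A total column would also need more than one denominator: subjects for AEs, and eyes, by visit where applicable, for biomicroscopy. Finally, SAP sections 3 and 7 and any table shells are not available here, so the absence of a pooled table from the visible text is weak evidence that none is planned.

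**Conclusion.** No change to the plan follows. Carried out as written, the safety analysis gives sound descriptive results. The pooled DD T2 incidence can be recovered exactly from the three columns, detection of events is the same, and no test, visible planned interval or decision rule depends on the layout. A total column would print a sum that the reader can already form; it is a reasonable option for the table shells, as is a pointer from SAP section 5 to Protocol 6.8.

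The contrast of 12.7% with 4.4% is not the size of a fault, because it describes an interval outside the visible plan. The conclusion rests on three things: each subject belongs to one parallel group only, counts are reported with the percentages, and safety stays descriptive. The documents state the last two, and the first follows from randomization to a single sequence.

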	3. Day 8 (-1/+2 days) follow-up Lens 2/Exit			
Test Product Details	Primary component/material			
	Product Name	DD T2		
	LID Number	LID 006841		
	Manufacturer	Alcon		
	Other	The lenses will be available in		
		-1.00 D to -6.00 D (0.25 D steps)		
Control Product 1	Primary component/material	senofilcon A		
Details	Product Name	Oasys 1-Day		
	LID Number	LID 009601		
	Manufacturer	Johnson and Johnson Vision		
	Other	The lenses will be available in		
		-1.00 D to -6.00 D (0.25D steps)		
Control Product 2	Primary component/material	stenfilcon A		
Details	Product Name	MyDay		
	LID Number	LID 009602		
	Manufacturer	CooperVision		
	Other	The lenses will be available in		
		-1.00 D to -6.00 D (0.25 D steps)		
Control Product 3	Primary component/material	etafilcon A		
Details	Product Name	Moist		
	LID Number	LID 009603		
	Manufacturer	Johnson and Johnson Vision		
	Other	The lenses will be available in		
		-1.00 D to -6.00 D (0.25 D steps)		
Inclusion Criteria	1. Subject must be at least 18	years of age.		
	2. Subject must be able to und	derstand and must sign an ICF that has		
	been approved by an IRB.			
	3. Successful wear of daily di	sposable spherical soft contact lenses in		
	both eyes for a minimum o	f 5 days per week and 8 hours per day		
	during the past 3 months.			
	4. Manifest cylinder ≤ 0.75 D	 		
	5. BCVA 20/25 or better in each eye.			
		stop wearing their habitual contact		
	lenses for the duration of study participation.			
Exclusion Criteria	1. Any anterior segment infection, inflammation, or abnormality or			
	disease (including systemic) that contraindicates contact lens wear,			
	as determined by the Inves	_		
	1	2. Any use of systemic or ocular medications for which contact lens		
		ted, as determined by the Investigator.		
		ry or plan to have refractive surgery		
	during the study or irregular cornea in either eye.			

Document: TDOC-0054506 Version: 1.0; CURRENT; Most-Recent; Effective

Status: Effective Page 5 of 38

Status: Effective	1 agc 3 01 36
	4. Ocular or intraocular surgery (excluding placement of punctal plugs) within the previous 12 months or planned during the study.
	5. Biomicroscopy findings at screening that are moderate (Grade 3) or
	higher and/or corneal vascularization that is mild (Grade 2) or higher.
	6. Current or history of pathologically dry eye in either eye that, in the
	opinion of the Investigator, would preclude contact lens wear.
	7. Current or history of herpetic keratitis in either eye.

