Status: Effective Page 17 of 38

5.1.2 Visit 2, Week 1 [Day 8 (-1/+2 Days)] – Follow-Up Lens 1/Dispense Lens 2

1	Obtain information on any changes in medical health and/or the use of concomitant medications.
2	Record any device deficiencies or AEs including those associated with changes in concomitant medication dosing, which are observed or reported since the previous visit(s).
3	Review subject compliance with lens wear and adjunct product usage.
4	Administer Subjective Questionnaire to assess: Subjective overall quality of vision, OU Subjective overall quality of vision, OU

[figure not shown]
Document: TDOC-0054506 Version: 1.0; CURRENT; Most-Recent; Effective

Status: Effective Page 18 of 38

Status.	tus. Effective			
5	Evaluate the study lenses by performing the following:			
	Snellen VA with study lenses (OD and OS, at distance)			
6				
7	Perform slit-lamp biomicroscopy (without contact lenses) to evaluate the following:			
	Limbal hyperemia			
	Bulbar hyperemia			
	Corneal staining			
	Conjunctival staining			
	Palpebral conjunctival observations			
	Corneal epithelial edema			
	Corneal stromal edema			
	Corneal vascularization			
	Conjunctival compression/indention			
	• Chemosis			
	Corneal infiltrates			
	Other findings			
8	Based upon the randomized treatment sequence assignment, have the subject insert			
	the Lens 2 study lenses to be evaluated. Note: Keep all lidding foils of lenses used during lens fit process for study lens			
	accountability.			
9				
10	Evaluate the study lenses by performing the following:			
	Snellen VA with study lenses (OD and OS, at distance)*			
	Over-refraction if necessary to determine the best contact lens-corrected VA			
	and final study lens power(s)			
	* VA w/study lenses must be 20/40 OU or better for subject to leave the office			

Document: TDOC-0054506 Version: 1.0; CURRENT; Most-Recent; Effective

Status: Effective Page 19 of 38

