5.3 Statistical Methods for Safety Analyses

The analysis set for all safety analyses is the safety analysis set as defined in Section 2.1. Baseline will be defined as the last measurement prior to exposure to study lenses on Visit 1. Safety variables will be summarized descriptively.

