5.3.2 Biomicroscopy Findings/Slit Lamp Examination

The following tables and supportive listings will be provided:

Document: TDOC-0054657 Version: 1.0; CURRENT; Most-Recent; Effective

Status: Effective

- Frequency and Percentage for Biomicroscopy Findings by Visit
- Incidence of Increased Severity by 2 or More Grades in Biomicroscopy Findings
- Listing of Subjects With Other Biomicroscopy Findings
- Listing of Subjects With Increased Severity by 1 Grade in Biomicroscopy Findings
 [This listing will include all relevant visit within the crossover period]
- Listing of Subjects With Increased Severity by 2 or More Grades in Biomicroscopy Findings [This listing will include all relevant visits within the crossover period]
- Listings of Subjects with Infiltrates

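### Cheap improvement (minor): split the Lens 2 count of 2-grade biomicroscopy increases by the grade recorded at Visit 2, just before Lens 2 goes in

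*Protocol*

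**What the plan says.** Protocol 6.8 makes biomicroscopy one of three safety endpoints. Each parameter is tabulated by grade, and for each parameter the eyes with "an increase of ≥ 2 grades from Baseline (Visit 1) to any subsequent visit will be presented". SAP 5.3 fixes the reference for all safety analyses: "Baseline will be defined as the last measurement prior to exposure to study lenses on Visit 1".

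On which lens a finding belongs to, Protocol 6.2.1 says: "For treatment-emergent safety analyses, subjects/eyes will be categorized under the actual study lenses exposed". SAP 2.1 says that "subjects/eyes will be categorized under the actual study lens exposed in the corresponding lens sequence". Protocol 6.8 adds that DD T2 data are shown separately for each control group.

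Protocol 5.1.2 (Visit 2) puts the lens-free slit-lamp examination at step 7. At step 8 the subject inserts "the Lens 2 study lenses to be evaluated". No washout is scheduled.

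SAP 5.3.2 names two tables by title only: grade frequencies by visit, and "Incidence of Increased Severity by 2 or More Grades in Biomicroscopy Findings". For adverse events, SAP 5.3.1 has a rule on timing: "Each AE will be summarized under the exposed lens based upon the event onset date/time", until the next lens starts. Biomicroscopy has no such rule.

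Protocol 6.8 also plans a listing with the data from every visit for each eye that meets the 2-grade criterion. SAP 5.3.2 limits the matching listing to the visits that are relevant in the crossover period, which is less clear.

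**The concern.** Take an eye graded 0 at Visit 1, 2 after Lens 1 and 2 after Lens 2 (0-2-2). Measured from Visit 1, it meets the criterion at both follow-ups. Under the lens-exposed rule, the Visit 2 finding goes to Lens 1 and the Visit 3 finding to Lens 2. The Lens 2 finding may be nothing more than what Lens 1 left behind, and no planned table would show that. The by-visit table gives grade frequencies at each visit but does not link an eye's two follow-up grades.

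The objective is a comparison of lenses, and with no safety tests planned, the descriptive tables are what a reader compares. If one lens causes a sign more often, carry-over into the other lens's column makes the two look more alike than they are.

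**Working it through.** **Which signs are affected.** Signs reported as adverse events already go to one lens under SAP 5.3.1.

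- Vascularization: exclusion criterion 5 bars findings of Grade 3 or "higher and/or corneal vascularization that is mild (Grade 2) or higher". Entry grade is therefore below 2, a 2-grade rise ends at Grade 2 or more, and Protocol 7.1 makes neovascularization of Grade 2 or more reportable. All such rises are covered.
- Corneal staining: Protocol 7.1 applies from Grade 3. Rises from 1 or 2 are covered; a rise from 0 to 2 is not covered by this trigger.
- Infiltrates: symptomatic events are covered by Protocol 7.1.
- Any sign: under Protocol 7.2, an unfavourable change that the Investigator judges clinically relevant is an adverse event.

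What remains is 2-grade rises outside the Protocol 7.1 triggers that the Investigator does not judge clinically relevant.

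**Model.** The documents state no rate, so there is no figure to reproduce and every rate below is an assumption. Let pC and pT be the proportions of eyes reacting to control and to DD T2, p11 the proportion reacting to both, and q the chance that a Lens 1 sign persists to Visit 3, independent of the reaction to Lens 2. Findings count under the lens worn before each visit, and the two sequences of a control group are pooled 1:1.

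- DD T2 worn first: pT. DD T2 worn second: pT + q(pC − p11).
- Pooled: T = pT + 0.5q(pC − p11), and likewise C = pC + 0.5q(pT − p11).
- Difference: C − T = (pC − pT)(1 − q/2). The joint rate cancels. If pC = pT, no false difference arises.

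**Numbers.** The target of 60 completers over 6 sequences gives 10 subjects, or 20 eyes, per sequence, and 40 eyes per lens in each control group. With pT = 0, carry-over occurs only in the control-first sequence. Expected carried-over eyes are 20 × pC × q. The chance of at least one is 1 − (1 − pC·q)^20 if eyes are independent, or 1 − (1 − pC·q)^10 if both eyes of a subject react together.

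| pC, pT | q | Difference shown (points) | Expected eyes | Chance of at least one, independent eyes | Chance, both eyes together |
|---|---|---|---|---|---|
| 5%, 0% | 0 | 5.0 | 0 | 0% | 0% |
| 5%, 0% | 0.25 | 4.4 | 0.25 | 22% | 12% |
| 5%, 0% | 0.50 | 3.8 | 0.50 | 40% | 22% |
| 5%, 0% | 0.75 | 3.1 | 0.75 | 53% | 32% |
| 1%, 0% | 0 | 1.0 | 0 | 0% | 0% |
| 1%, 0% | 0.25 | 0.88 | 0.05 | 5% | 2% |
| 1%, 0% | 0.50 | 0.75 | 0.10 | 10% | 5% |
| 1%, 0% | 0.75 | 0.63 | 0.15 | 14% | 7% |

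One carried-over eye adds 1/40 = 2.5 points to the Lens 2 product's column. If the table is shown by sequence instead, only the control-first sequence is affected: at pC = 5% it shows 1.25%, 2.5% or 3.75% for DD T2 at q = 0.25, 0.50 or 0.75, although the assumed DD T2 rate is 0%.

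**What a split would show.** Among Lens 2 findings, new since Visit 2 = pT − p11, and already present = p11 + q(pC − p11). For 0% against 5%, new is 0% and already present is 1.25%, 2.5% or 3.75%, so the carry-over is visible. With 5% on both lenses and independent reactions, p11 = 0.25% and new = 4.75%. If the same eyes react to both, p11 = 5% and new = 0%, although Lens 2 causes the sign in 5% of eyes.

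**The case against.** The strongest reply is that little is left to repair. Protocol 7.2 sends every change judged clinically relevant to adverse event reporting, whatever its grade. The all-visits listing shows persistence eye by eye, and with well under one expected carried-over eye per sign in the cases above, reading a listing may be enough. The lens-exposed rule already points to the lens worn before each visit. Nothing is tested, and no decision rests on the table.

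Most of this stands and is why the point is minor. In particular, a reader might infer that low-grade signs such as staining from 0 to 2 never reach adverse event reporting; Protocol 7.2 does not support that. A listing, however, does not change the percentages in the table, and the SAP wording leaves open whether the Visit 2 grade will appear in it.

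A further objection is that sorting Lens 2 findings only by whether the criterion was met at Visit 2 would mislead: an eye graded 0-2-3 would be called already present although it worsened on Lens 2. That is correct, and it is why the split below has three parts.

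**Conclusion.** The point holds as a minor improvement to reporting. Visit 1 is the only reference, the Visit 2 grade is collected at the right moment and not used, and no planned table separates new Lens 2 findings from those already there. Under the assumed model, the lens difference shrinks by 1 − q/2: by an eighth at q = 0.25, by a quarter at q = 0.50, and not at all at q = 0. This rests on the by-lens layout, pooled sequences, and rates and persistence that the documents do not give.

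Three stronger readings are not supported.

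- A reader might infer that the plan states that a persisting sign counts twice. It does not. This is the natural reading of the lens-exposed rule, but the wording on any later visit could also mean one count per eye, and the plan would then not say which lens receives it.
- A reader might infer that the Visit 1 reference is an error. It is not. Visit 1 gives the only grade taken before any study lens. Replacing it with Visit 2 would hide Lens 2 reactions in eyes that react to both lenses.
- A reader might infer that the table would create a false difference. Under the model it does not; it can only narrow a real one.

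The safety analysis is descriptive and the SAP sets no success criterion, so only the reading of this table is affected.

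**What to change.** Keep the Visit 1 comparison as the main table. Add to Protocol 6.8 and SAP 5.3.2, in words such as these:

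> Increases of 2 or more grades from Visit 1 are tabulated under the lens worn before each visit. For Lens 2, the count for each parameter is divided into: (a) criterion not met at the Visit 2 examination before Lens 2 insertion (new since Visit 2); (b) criterion already met at Visit 2, and grade not higher at the Lens 2 follow-up; (c) criterion already met at Visit 2, and grade higher at the Lens 2 follow-up (worsened on Lens 2).

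Footnote: category (b) cannot tell a sign that persisted from one that Lens 2 produced again, and category (a) can include eyes with part of the rise on Lens 1, such as 0-1-2.

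Change the 2-grade listing in SAP 5.3.2 to show every visit for the affected eyes, as Protocol 6.8 does.

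The cost is one sentence on attribution, one split of an existing count, one footnote and one change of wording. No visit, examination or data field is added. The drawback is that (a) under-counts Lens 2 when the same eyes react to both lenses, down to 0% in the example above, so the split must stand beside the total and not replace it.
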